Identifiable brain research data are stored on a secure database located on the internal PET Center Network. The PET network is protected by a Cisco PIX firewall operated by ITS. All research data are backed up nightly to a Dell PV-136T library wit 4 IBM Ultrium-TD2 tape drives using the backup software Legato Networker 7.3 from EMC. Human subjects enrolled in the study are assigned a subject-specific random identifier. Subject identifiers and the means to link the subject names and codes with the research data are stored in separate locations within the database. The software of the database limits the ability to connect the random identifier to the actual subject identification information to research team members only. Access to the database is password protected and each research team member is required to have a unique ID and password to gain access to the database. Authorized users employ their netid and authentication is performed using Yale's central authentication server. Users always access research data through the random identifier only.

e. What will be done with the data when the research is completed? Are there plans to destroy the identifiable data? If yes, describe how, by whom and when identifiers will be destroyed. If no, describe how the data and/or identifiers will be secured.

The data will be stored in locked filing cabinets and on the password-protected secure database on the internal Yale University PET Center Network for at least 7 years, accessed only by study personnel.

f. Who will have access to the protected health information (such as the research sponsor, the investigator, the research staff, all research monitors, FDA, Yale Cancer Center Data and Safety Monitoring Committee (DSMC), SSC, etc.)? (please distinguish between PHI and de-identified data)

Only very select, authorized individuals in the PET center (appointment scheduler, nurse, nuclear medicine technician, administrator in charge of billing and patient reimbursement) and the PI will have access to the key that identifies patient codes. Relevant research staff at CMHC will also have access to the information entered into the participant's CMHC medical record.

No external agency (other than the FDA) will have access to the data.

g. If appropriate, has a Certificate of Confidentiality been obtained?

A Certificate of Confidentiality from NIH will be obtained prior to study enrollment. With this Certificate, the researchers cannot be forced to disclose information that may identify subjects, even by a court subpoena, in any federal, state, or local civil, criminal, administrative, legislative, or other proceedings. The Certificate does not imply approval or disapproval of the project by the Secretary of DHHS. It adds special protection for the research information about subjects. The researchers will use the Certificate to resist any demands for information that would identify subjects, except as explained below. The Certificate cannot be used to resist a demand for information from personnel of the United

Page 44 of 51

APPROVED BY THE YALE UNIVERSITY IRB 10/25/2023

States Government that is used for auditing or evaluation of federally funded projects or for information that must be disclosed in order to meet the requirements of the federal Food and Drug Administration (FDA). A Certificate of Confidentiality does not prevent subjects or subject family members from voluntarily releasing information about the subject or their involvement in this research. If an insurer, employer, or other person obtains written consent from the subject to receive research information, then the researchers may not use the Certificate to withhold that information.

h. Are any of the study procedures likely to yield information subject to mandatory reporting requirements? (e.g. HIV testing – reporting of communicable diseases; parent interview -incidents of child abuse, elderly abuse, etc.). Please verify to whom such instances will need to be reported.

The Certificate of Confidentiality does not prevent the researchers from disclosing voluntarily, without subject consent, information that would identify the subject as a participant in the research project under the following circumstances: In the event of relevant discovery related to events of abuse, identified health risks, or threats to self or others, as related to the health and safety of the public and/or individual study participants, a report will be made to the relevant agencies and authorities to be conducted as outlined and mandated by HIC guidelines, and Federal, State, and Local Statutes.

SECTION VIII: POTENTIAL BENEFITS

Potential Benefits: Identify any benefits that may be reasonably expected to result from the research, either to the subject(s) or to society at large. (Payment of subjects is not considered a benefit in this context of the risk benefit assessment.)

These studies are not of direct benefit to subjects. This study will help advance knowledge regarding the brain's dopamine and beta-endorphin response to drug addiction.

In the long term, the knowledge mentioned above can guide scientists in their efforts to develop new treatments for drug addiction. There is no direct benefit to these subjects. They will be able to withdraw from the study at any time.

SECTION IX: RESEARCH ALTERNATIVES AND ECONOMIC CONSIDERATIONS

1. Alternatives: What other alternatives are available to the study subjects outside of the research?

The alternative to participation in this research protocol is to not participate. Subjects will be informed that they are free to choose not to participate and, if they do agree to become a subject, they will be free to withdraw from the study at any time during its course. They will also be informed that if they choose not to participate or if they withdraw, it will not adversely affect their relationship with their doctors or the hospital (per the consent form).

2. Payments for Participation (Economic Considerations): Describe any payments that will be made to subjects, the amount and schedule of payments, and the conditions for receiving this compensation.

The subjects will be compensated for their time commitment and inconveniences necessary for completing the study. Subjects will have no financial responsibilities for any portion of the study.

For all aims, compensation will be the following:

- \$400 for each PET scan (i.e., up to \$800 if participating in both scans)
- \$50 for the MRI scan.
- \$50 for an arterial line (aim 3)
- \$100 bonus upon completion of all study procedures

Subjects participating will receive a total of up to \$950 for Aim 1, and up to \$1000 for Aim 3. This includes a \$100 completion bonus after finishing their participation in each aim (1 MRI and up to 3 PET scans). Subjects who participate in the Probabilistic Reward Task may also be compensated for the amount that they "win" during the task up to 50\$. Subjects who complete cogstate will received 40\$. may also receive \$10 each time they participate in the Cold Pressor Task

Subjects will be paid either by check, and are advised to allow 4-6 weeks for receipt of payment, or they will be given a credit card or cash. In addition, subjects will be provided with a light lunch, valued at no more than \$10. They will also be reimbursed for parking on their PET scan days, or they may be compensated for reasonable transportation costs, including taxi fees to and from scans.

Cancellations: If a PET scan should be cancelled by the PET Center for a reason outside of the subject's control (i.e. radiotracer synthesis failure) the subject will be paid \$50 minimum, or a higher amount not to exceed the payment for a full scan day. The amount of the payment for cancellation will be based on the subject's length of participation on that scan day prior to the cancellation, and will be up to the discretion of the PI.

3. **Costs for Participation (Economic Considerations):** Clearly describe the subject's costs associated with participation in the research, and the interventions or procedures of the study that will be provided at no cost to subjects.

Subjects will not be financially responsible for tests, examinations, and medical care provided to them during their participation in this study.

- 4. In Case of Injury: This section is required for any research involving more than minimal risk.
 - a. Will medical treatment be available if research-related injury occurs?
 - b. Where and from whom may treatment be obtained?
 - c. Are there any limits to the treatment being provided?
 - d. Who will pay for this treatment?

Page 46 of 51

e. How will the medical treatment be accessed by subjects?

Medical treatment will be offered to the subjects for any physical injuries that they receive as a result of participating in this research. However, the subject or his/her insurance company is responsible for the cost. Federal regulations require that subjects be told that if they are physically injured, no additional financial compensation is available.

Treatment may be provided by Yale-New Haven Hospital or any health care provider chosen by the study subjects. The study team will provide assistance to the study subjects in accessing medical treatment through referrals, or the study subjects may choose to access treatment on their own.

References

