humans¹. In addition, it has been hypothesized that DA influences reward "wanting", while the opioid system governs reward "liking"², both of which are critical for understanding neurochemical processes underlying compulsive drug use. These findings in animals need to be confirmed in humans to validate the animal models, to improve our understanding of the neurochemistry of drug abuse, and so that we can test new medications in humans. With PET we can noninvasively, and now dynamically, measure neurotransmitter changes in response to drugs of abuse in humans. This investigation will utilize a system previously developed by our group for imaging and modeling DA release in humans from cigarette smoking in the PET scanner. Our experimental and analytical techniques are sensitive enough to detect moderate increases in striatal DA (in magnitude and spatial extent) that are expected with marijuana. Our model is also uniquely able to capture the *temporal profile* of *brief* DA responses. The goals of this study are to extend our paradigm to additional drugs of abuse (marijuana) and to extend our technology to an additional neurotransmitter system (opioid-ergic) with the same drugs of abuse (tobacco, marijuana). This will allow us to determine the spatio-temporal patterns of combined DA and beta-endorphin fluctuations associated with drugs of abuse in the living human brain.

Aim 1: To examine the magnitude, location and timing of drug-induced dopamine release.

- **a.** Tobacco smokers (n=20) will be imaged with [¹¹C]raclopride PET, after overnight abstinence from tobacco. Subjects will smoke their preferred brand of cigarette during the PET scan.
- **b.** Marijuana smokers (n=20) will be imaged with [¹¹C]raclopride PET, after overnight abstinence from marijuana. Subjects will smoke a marijuana cigarette during the PET scan.

Aim 2: To examine the magnitude, location and timing of drug-induced beta-endorphin release. *We will attempt to use the same subjects from Aim 1 for Aim 2 (Marijuana Exposed Healthy Controls are the exception)

- **a.** Tobacco smokers (n=20) will be imaged with [¹¹C]carfentanil PET, after overnight abstinence from tobacco smoking. Subjects will smoke their preferred brand of cigarette before or during the drug condition PET scan.

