- **b.** Marijuana smokers and Marijuana Exposed Healthy Controls (n=20) will be imaged with [¹¹C]carfentanil PET, after overnight abstinence from marijuana smoking. Subjects will smoke a marijuana cigarette before or during the drug condition PET scan.

Aim 3: To examine the magnitude, location and timing of marijuana-induced dynorphin release. Cannabis has diverse effects on the endogenous opioid system. We will image Marijuana Smokers and Marijuana Exposed Healthy Controls (n=20) with [¹¹C]EKAP PET, after overnight abstinence from marijuana smoking. Subjects will smoke a marijuana cigarette before or during the drug condition PET scan.

2. **Background:** Describe the background information that led to the plan for this project. Provide references to support the expectation of obtaining useful scientific data.

Page 9 of 51

The neurochemistry of drug addiction. Drug addiction is a widespread public health issue, affecting at least one quarter of the adult U.S. population. A key process of chronic drug use is the transition from voluntary to compulsive use in spite of adverse consequences. The rewarding aspects of drug abuse are known to be critical to both the initiation, i.e., voluntary, and maintenance of drug use⁴. Reward processes are primarily influenced by the DA and opioid neurotransmitter systems. It has been hypothesized that DA influences reward "wanting", while the opioid system governs reward "liking"², both of which are critical for understanding neurochemical processes underlying compulsive drug use. For example, initial drug seeking for the pleasurable aspects of the drug ("liking") often gives way to habitual drug use ("wanting"), particularly in response to drug cues, despite individuals reporting little pleasure from the drug itself⁵. While much preclinical work has studied dopamine-opioid interactions in reward response^{6,7}, extending this work to study the neurochemistry of reward response in *clinical* substance abuse disorders has been limited.

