This study will recruit drug users (tobacco or marijuana) to participate in one magnetic resonance imaging scan (MRI),one [¹¹C]raclopride PET scan, two [¹¹C]carfentanil PET scans, and two[¹¹C]EKAP PET scans (for marijuana users/marijuana exposed). If subjects have never been in a PET scanner, they may participate in a brief "mock" PET scan session prior to their actual scan to familiarize them with the environment (reduce the novelty) and if they are a smoker, to familiarize them with the mechanics of smoking in the scanner.

Aim 1. To examine the magnitude, location and timing of drug-induced dopamine release.

- **a.** Tobacco smokers (n=20) will be imaged with [¹¹C]raclopride PET, after overnight abstinence from tobacco smoking. Subjects will smoke their preferred brand of cigarette during the PET scan.
- **b.** Marijuana smokers (n=20) will be imaged with [¹¹C]raclopride PET, after overnight abstinence from marijuana smoking. Subjects will smoke a marijuana cigarette during the PET scan.

Aim 2. To examine the magnitude, location and timing of drug-induced beta-endorphin release. *We will attempt to use the same subjects from Aim 1 for Aim 2. (Marijuana Exposed Healthy Controls are the exception)

- **a.** Tobacco smokers (n=20) will be imaged with [¹¹C]carfentanil PET, after overnight abstinence from tobacco smoking. Subjects will smoke their preferred brand of cigarette before or during the drug condition PET scan
- **b.** Marijuana smokers and Marijuana Exposed Healthy Controls (n=20) will be imaged with [¹¹C]carfentanil PET, after overnight abstinence from marijuana smoking. Subjects will smoke a marijuana cigarette before or during the drug condition PET scan.

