Up to 110 subjects (55 men, 55 women) will participate in the study. According to census figures, minority groups comprise approximately 50% of the population of New Haven (36.1% African-American, 13.2% Hispanic, 0.3% Native American, 2.4% Asian, and 4.1% other). While we prefer to have 60 subjects complete both Aim 1 and Aim 2, we anticipate up to a 50% drop out rate between scans so we are allowing for the possibility having 110 subjects participate.

All subjects will be 18-55 years of age and physically healthy. All research subjects will be recruited under guidelines of the Yale University Institutional Review Board (Human Investigation Committee). Subjects will be recruited from the community at large via IRB-approved advertising (television, newspaper, postings in community locations, Craigslist, Facebook). All participants will be screened initially on the telephone by a research assistant who will schedule the initial intake assessment. The screening and scanning sessions will involve psychological tests in the form of rating scales and questionnaires. These are all noninvasive questionnaires, e.g., to assess mood and craving, and should add no risk.

6. **Subject classification:** Check off all classifications of subjects that will be specifically recruited for enrollment in the research project. Will subjects who may require additional safeguards or other considerations be enrolled in the study? If so, identify the population of subjects requiring special safeguards and provide a justification for their involvement.

Children	🔀 Healthy	Fetal material, placenta, or dead fetus
Non-English Speaking	Prisoners	Economically disadvantaged persons
Decisionally Impaired	Employees	Pregnant women and/or fetuses
Yale Students	\boxtimes Females of ch	nildbearing potential

NOTE: Is this research proposal designed to enroll children who are wards of the state as potential subjects? Yes No (If yes, see Instructions section VII #4 for further requirements)

7. Inclusion/Exclusion Criteria: What are the criteria used to determine subject inclusion or exclusion?

Page 21 of 51

General Inclusion Criteria:

- 1. Men and women, aged 18-55 years
- 2. Able to read and write English and give voluntary written informed consent
- 3. Not treatment seeking or using treatment medications

Tobacco Smokers

- 1. Have a Fagerström Test for Nicotine Dependence (FTND) rating of at least 3.
- 2. Have been using at least 7 cigarettes per day for at least 1 year

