- 3. Carbon monoxide levels > 10 ppm during intake evaluation
- 4. Urine cotinine levels of > 150 ng/mL during intake evaluation
- 5. Are not current users of marijuana or other illicit drugs

Marijuana Smokers

- 1. Meet DSM-V criteria for cannabis use disorder based on the structured clinical interview diagnostic (SCID) or regular cannabis use of >5 times/week
- 2. Test positive for THC
- 3. Have been smoking cannabis on a regular basis for \geq 1 year

Marijuana Exposed Health Controls

1. Do not meet DSM-V criteria for cannabis use disorder based on the structural clinical interview diagnostic (SCID)

2. Have used cannabis in the past recreationally

General Exclusion Criteria:

- 1. Current significant medical condition such as neurological, cardiovascular, endocrine, renal, liver, or thyroid pathology.
- 2. History of or current neurological or significant psychiatric disorder such as schizophrenia or bipolar disorder (DSM-IV Axis 1).
- 3. History of significant head trauma.
- 4. Women who are pregnant or nursing, or fail to use one of the following methods of birth control unless she or partner is surgically sterile or she is postmenopausal (hormone contraceptives [oral, implant, injection, patch, or ring], contraceptive sponge, double barrier [diaphragm or condom plus spermicide], or IUD).
- 5. Regular or current significant use of any prescription, herbal or illegal psychotropic medications (e.g., antidepressants, antipsychotics, anxiolytics, ecstasy) in the past 6 mo, with no current illegal drug use confirmed by urine toxicology (marijuana when relevant).
- 6. Significant substance misuse (including alcohol, and excluding cannabis and marijuana when relevant) that in the PI's determination interferes with the study results or safety of the subject.
- 7. Have MRI-incompatible implants and other contraindications for MRI, such as a pacemaker, artificial joints, non-removable body piercings, claustrophobia, etc.
- 8. Subjects with history of prior radiation exposure for research purposes within the past year such that participation in this study would place them over FDA limits for annual radiation exposure. This guideline is an effective dose of 5 rem received per year.

Page 22 of 51

- 9. Subjects with current, past or anticipated exposure to radiation in the work place within one year of proposed research PET scans.
- 10. Subjects with history of IV drug use which would prevent venous access for PET tracer injection.

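### The preferred 60 subjects completing both Aim 1 and Aim 2 cannot come from Aim 1 cells of 20 tobacco and 20 marijuana smokers; the most possible is 40

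*Combined protocol and SAP*

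**What the plan says.** All references are to the combined protocol and SAP.

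- **Section IV, item 5 (Subject Population)** sets the dual-aim goal and the dropout expected from one scan to the next: "While we prefer to have 60 subjects complete both Aim 1 and Aim 2, we anticipate up to a 50% drop out rate". It then draws the consequence for enrolment: "so we are allowing for the possibility having 110 subjects participate". The same item caps the whole study at 110. Section VI, item 1 (Targeted Enrollment) repeats 110, from 250 screened.
- **Section IV, items 1 and 3.1** give Aim 1 two cells, in the same terms both times: "Tobacco smokers (n=20) will be imaged with" raclopride PET, and "Marijuana smokers (n=20) will be imaged with" raclopride PET.
- **Aim 2** has 20 tobacco smokers (2a) and a mixed marijuana cell (2b): "Marijuana smokers and Marijuana Exposed Healthy Controls (n=20) will be imaged with" carfentanil PET. On overlap with Aim 1, item 3.1 says: "We will attempt to use the same subjects from Aim 1 for Aim 2. (Marijuana Exposed Healthy Controls are the exception").
- **Section IV, item 3.1** describes recruitment as "This study will recruit drug users (tobacco or marijuana"); the sentence later mentions marijuana-exposed people in connection with the EKAP scans.
- **Section IV, item 7** gives criteria for three groups: tobacco smokers, marijuana smokers and "Marijuana Exposed Health Controls". Tobacco smokers may not be current marijuana users, so nobody can fill a place in both Aim 1 cells.

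**The concern.** The number of people who provide both a dopamine and an opioid measurement cannot exceed the number in Aim 1. The listed Aim 1 cells sum to less than the stated goal, and no third Aim 1 group is described anywhere.

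The Background (Section IV, item 2) presents imaging both systems in the same subjects as a feature of the proposal. Item 5 is the only place that states outright how many subjects should provide both. It is also the only rationale given for the enrolment ceiling, because Section IV, item 12 contains no sample-size calculation. As written, a reader cannot tell whether the goal is 40 or 60 dual-aim subjects, or when recruitment towards it is complete. The investigator rates the study as greater than minimal risk because of radiation, so the number exposed should rest on figures that agree.

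**Working it through.** **Inputs**

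| Quantity | Value | Source |
|---|---|---|
| Preferred completers of both aims | 60 | IV.5 |
| Dropout between scans | up to 50% | IV.5 |
| Maximum participants | 110 | IV.5, VI.1 |
| Aim 1a, tobacco smokers | 20 | IV.1, IV.3.1 |
| Aim 1b, marijuana smokers | 20 | IV.1, IV.3.1 |
| Aim 2a, tobacco smokers | 20 | IV.1, IV.3.1 |
| Aim 2b, marijuana smokers and exposed controls | n=20, combined or per group not stated | IV.1, IV.3.1 |

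**Step 1: try to reproduce 60.** Dual-aim maximum = min(Aim 1a, Aim 2a) + min(Aim 1b, marijuana smokers in Aim 2b).

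- *2b read as 20 per group.* Aim 2 holds 20 + 20 + 20 = 60. Twenty of these are controls who are not Aim 1 subjects, so the dual-aim maximum is min(20, 20) + min(20, 20) = 40.
- *2b read as 20 combined.* Aim 2 holds 20 + 20 = 40. With at least one control enrolled, fewer than 20 marijuana smokers remain and the maximum is below 40. For illustration, an assumed 10/10 split gives 20 + 10 = 30.

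Neither reading gives 60. The only 60 in the cells is the Aim 2 head count under the per-group reading, and that is not a count of people completing both aims.

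**Step 2: size of the gap.** 60 − 40 = 20, and 20/60 = 33%.

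**Step 3: starters or completers.** The 40 treats n=20 as completers, the generous reading. If n=20 counts people who start Aim 1, 50% dropout leaves 40 × 0.5 = 20. Only a reading of n=20 as a minimum could reach 60, and the text does not say that.

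**Step 4: does 110 follow from 60?** Treat dropout d as one attrition step per person.

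- Starters needed: 60/(1 − 0.5) = 120, which is 10 above 110.
- Adding 50% to the target instead: 60 × 1.5 = 90. This does not give 110 either.
- Completers from 110 at the bound: 110 × 0.5 = 55, which is 5 short of 60.
- Dropout at which 110 leaves exactly 60: (110 − 60)/110 = 45.5%.

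So 110 delivers 60 if dropout is about 45.5% or less, and falls short only between there and the stated bound. These figures also assume that all 110 places go to dual-aim subjects. They cannot, because 110 is the ceiling for the whole study and must hold the exposed controls. It must also hold any participants who enter Aim 3 only. The documents do not say there will be such people, but Aim 3 has its own authorization form (VI.11) and payment total (IX.2).

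**Step 5: does a target of 40 fit?** 40/(1 − 0.5) = 80 starters, and 110 − 80 = 30 places remain for exposed controls and any Aim 3-only participants.

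**The case against.** The best reply is that little rests on the 60. It is worded as a preference, and overlap between the aims is best-effort. No analysis in Section IV, item 12 uses a dual-aim count, and no eligibility or safety limit depends on it. If the Aim 1 cells are correct, the repair is a change of text. All of this is true, and it limits the consequence. It does not remove the contradiction: the listed cells cannot meet the preference, yet that preference is the stated reason for the ceiling.

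A second reply is that the 110 is a loose allowance. The plan speaks of up to 110 participants and up to 50% dropout and does not claim an exact derivation; a rate of 45.5% or less lies inside that range. This is fair. The 55-against-60 point applies only at the bound and is secondary.

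Third, the plan never says whether n=20 means enrolled, completing or at least 20. That ambiguity is real, but treating n=20 as starters lowers the maximum, and nothing in the text supports a minimum.

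Finally, the 20 + 20 cells appear twice in the same form and the 60 only once, so the text leans towards the cells. It leans that way without settling which figure was meant.

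**Conclusion.** The concern holds. As the aims are written, at most 40 subjects can complete both Aim 1 and Aim 2, against a preferred 60: a gap of 20, or one third. If the Aim 2b n=20 combines smokers and controls, with at least one control enrolled, the maximum is below 40. The bound rests on reading the Aim 1 n=20 per cell as a target rather than a minimum, and on the stated exception for exposed controls.

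The ceiling is a lesser point. With one attrition step at the 50% bound, 110 yields at most 55 dual-aim completers, before any places are set aside for other participants. No prespecified test is affected. The plan should be corrected because its stated deliverable and its enrolment rationale disagree with its own cells.

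**What to change.** Reconcile the 60 in Section IV, item 5 with the Aim 1 cells. The sponsor must say which is intended.

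1. **If the cells are right:** restate the dual-aim target as at most 40, 20 per drug, and say that n=20 means completers. This needs 80 starters at 50% dropout, inside the existing 110. The cost is a text amendment to IV.5 and VI.1.
2. **If 60 is intended:** raise the Aim 1 cells in IV.1 and IV.3.1 by 20 in total so that they sum to at least 60. At 50% dropout, either raise the ceiling by at least 10, to 120 for dual-aim subjects alone, or state that 110 gives at most 55.

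In either case, state in IV.5 and VI.1 how many dual-aim completers 110 delivers at 50% dropout once places for exposed controls and any Aim 3-only participants are taken out. Also say whether n=20 in Aims 2b and 3 is combined or per group. That clarification does not close the gap between 60 and 40, but it is needed to fix the number of places left.
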